13.1 Inclusion criteria

- Patients will be considered eligible if all the following apply:
- People on the case load of selected community mental health services within each NHS site;
- Diagnosed with a severe mental illness (schizophrenia, other psychosis, bipolar affective disorder, schizoaffective disorder);
- In receipt of Care Programme approach;
- Are aged 18 and over;
- Willing to provide written informed consent;
- Able to provide written informed consent.

13.2 Exclusion criteria

Patients will be considered ineligible if one or more of the following apply:

- Acute exacerbation of their mental illness that precludes them from active participation (as indicated by hospitalisation and/or being under the crisis/home treatment team at the time of consenting);
- Severe physical illness that precludes them from active participation;
- Significant cognitive impairment (such as an organic brain disorder) as determined by case notes;
- Non-English speaker (adapting the intervention is currently beyond the scope of this study);

- Lacking capacity to consent (as guided by the Mental Capacity Act);
- Unable or unwilling to give written informed consent;
- Those on the Sex Offender Register.

14. Expected number of eligible participants

In previous studies of sexual health interventions for people with serious mental illness (Carey et al, 2004, Berkman 2007) approximately 50-60% of people screened were eligible; and of those eligible, around 40% consented to take part.

In our sites, if we assume we recruit from 2 community services with on average 300 patients on each team case load we could screen up to 600 per site. This means that there will be potentially 2400 people for screening over the whole study. Of these 1200 (50%) may fit with eligibility, and using a conservative estimate of 25% who then give informed consent, then we should be potentially able to recruit 300 (target is 100).

15. Participant recruitment

15.1 Method

Two routes to participant recruitment will be used for the trial in the four NHS Trusts, screening of caseloads and self-referral.

15.2 Caseload screening

Local researchers employed by the Clinical Research Network (CRN) based in each site's Research and development office will work with the Trust clinical staff to promote the study, and undertake case load screening for potentially eligible participants using the eligibility criteria outline above. Clinical staff in specific teams and services that have agreed to participate will be asked to distribute information to those identified as potentially eligible. This information pack will include an invitation letter, the Patient Information Sheet (PIS) and consent to contact form.

Completed consent to contact forms will be passed (either by fax, scanned or hard copy) onto the CRN research staff for eligibility screening at a local level. Eligibility screening will be carried out by CRN clinical study officers at each recruiting site.

15.3 Self-referral

Staff at clinical services in each recruiting site will be sent posters and leaflets about the study for them to display in the waiting areas of their team base. The information will contain an email, QR code and website address to the project website. This website has been designed to provide information about the study for staff and potential participant as well as other interested parties. The posters and leaflets will provide a brief description of the study and methods for contacting the local RESPECT research team directly. The RESPECT researchers will not approach or be present to give out leaflets themselves. By contacting the RESPECT research team directly we will assume the potential participant has implicitly agreed to contact by the research team and the consent to contact form will not be completed, however, a record of the contact and any contact information will be recorded by the research team. An information pack (to include an invitation letter, PIS and consent to contact form will be sent to anyone self-referring if they request. The local RESPECT research team will re-contact potentially eligible participants following the receipt of their pack to determine interest and determine eligibility. However, self-referring participants will be unable to participate the study without agreement from their case manager that there are no factors that could affect them participating. The potential participant will be informed that as a final aspect of eligibility we will have to check with their case manager but no information will be shared (other than their interest in taking part) and have self-referred to the research team. We are utilising this method of recruitment to ensure all potentially eligible participants have the opportunity to take part. The method of recruitment will be recorded to inform the most effective recruitment strategies for the main trial. We will establish a study email address specifically to manage enquiries regarding the study which will be administered by the RESPECT research team.

16. Eligibility assessment

All potentially eligible participants identified either by caseload screening or self-referral will be contacted by telephone to confirm their eligibility by staff employed by the Clinical Research Network at each site. For each potential participant an Eligibility and Screening Form will be completed. Once eligibility is confirmed the CRN researchers will inform the RESPECT researcher who will arrange a convenient time and venue to meet with the potential participant. The purpose of this meeting is to discuss the study in more detail, and to gain informed consent. As part of this process we will record of the number of people who received a pack, who gave consent to contact, method of recruitment and how many of those screened were eligible and consent will be recorded and used to populate the CONSORT flow chart.

Eligible patients who do not wish to take part (i.e. unwilling to give consent) and those found to be ineligible will go on to receive usual care from the service without prejudice.

Reasons for non-participation will be collected to inform future studies. Keyworkers will hand out feedback forms to those they discuss the study with, and who then decline to participate. We will send all people who returned a consent to contact form, a feedback form which asks questions about how they found the recruitment process.

17. Information regarding study

Eligible participants will be given an information pack inviting them to take part in the study either from the care coordinator at the NHS Trust or from the RESPECT team. If after reading the materials they are interested, they will be asked to return a completed consent to contact form. Once this form is received by the CRN researchers, then an eligibility screen will take place. If eligible and agree to meet the researcher, their contact details will be passed on to the RESPECT researcher. They will arrange to meet face to face with the potential participant. At this meeting, the RESPECT researcher will fully explain the study verbally, and give the patient the opportunity to ask questions. If the person is willing, then the researcher will invite the patient to participate. Written informed consent to be included in the trial will then be sought. Potential participants will be assured of confidentiality, what to expect after the study ceases and given contact details in case of complaint or need for further information. They will be informed that participation is not compulsory and that they can withdraw from the intervention and /or data collection at any time without affecting their care. They will also be informed that if randomly allocated to the sexual health intervention that they can withdraw from the intervention at any point but still have the option of staying in the study for the purposes of follow-up data collection. The PIS will meet the

requirements of the NHS ethics committees and will clearly present the potential positives and negatives associated with taking part in the trial.

18. Consent procedure

For those that agree to participate, the researcher will:

- Obtain written informed consent to participate in the trial;
- Conduct a baseline assessment;
- Telephone the York Trials Unit Freephone randomisation service or use the online system to randomise the patient (hereafter referred to as the participant);
- Inform the participant of their allocated group and the next steps in the trial;
- Provide a leaflet on local sexual health, family planning and domestic abuse services.

19. Definition for the End of Trial

End of study will be defined as the date at which the last participant has completed the study processes.

20. Trial Interventions

Participants will be randomised to receive treatment from a clinician trained in delivery of the manualised intervention:

1) Sexual Health Intervention: an initial appointment with one of the interventionists, followed by two further sessions in a maximum of 8 weeks.

The sexual health intervention has been developed during an earlier phase of work, which comprised of an analysis of available manuals, information about risk and unmet needs, public involvement involving service users, and consultation with therapists and service managers. The intervention will include a number of facets in order to provide a comprehensive intervention. One of the main aims of the intervention is to help a person to identify their needs in relation to sexual health and relationships, as well as how to access and use the appropriate services. The intervention will be delivered by a clinician employed within the NHS sites who has undertaken the RESPECT training. The intervention will be delivered face to face. Participants will receive the intervention in addition to treatment as usual (including access to local primary care and /or specialist sexual health services).

2) TAU: There is no specific service for people with SMI in terms of sexual health. Those participants randomised to receive TAU will continue to receive their usual care. Treatment as usual for sexual health (including contraception) would include the local primary care and/or specialist sexual health services. People using mental health services should have the same access to these services as the general population, and should be sign-posted or referred to these services if a sexual health need is identified within a mental health consultation.

21. Concurrent treatments

Wherever there is a need for medical treatment of a physical condition, surgical or psychiatric condition, these will be available through the usual processes. Such concurrent treatments will not affect study participation unless they preclude delivery of the study intervention or follow-up.

22. Randomisation

22.1 Treatment Allocation

Patients who fulfil the eligibility criteria, who provide written consent to take part in the study and provide baseline data will be eligible for randomisation. Randomisation, will be on a 1:1 basis using stratified block randomisation with stratification by centre and variable block sizes. Patients will be randomised by remote computer to either the sexual health intervention or TAU. This will be conducted using the remote secure randomisation service at York Trials Unit. This will be available as a web-based system (24 hours) and a telephone system (09:00 to 17:00, Monday to Friday, excluding Bank Holidays).

The following information will be collected at randomisation:

- Centre;
- Patient details including full name, gender, date of birth, NHS number, full postal address, contact telephone number(s) and email address;
- Confirmation that patient meets all the eligibility criteria;
- Confirmation that written informed consent has been obtained;
- Confirmation that all baseline data has been collected;
- Confirmation if they can be contacted for future studies.

23. Blinding

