3.1 Main objectives

The overall aim of the project is to establish the feasibility and acceptability of an evidence based intervention to promote sexual health, and to establish key parameters to inform a future main trial.

Objective 1: Assess the feasibility and acceptability of undertaking a trial by:

a) Quantitative assessment of numbers screened, number eligible and those agreeing to participate,

b) Qualitatively assessing feasibility and acceptability of randomisation process, as well as the intervention.

c) Quantitatively evaluate acceptability of the intervention by assessing retention in treatment (number of sessions attended)

d) Quantitatively evaluate acceptability of proposed method of data collection and data collection tools by assessing overall questionnaire response rates and for each data collection tool. *Objective 2:* Identify key parameters to inform the sample size calculation for the main trial: the standard deviation of the primary outcome measure, quantify the average caseload per therapist and tentatively explore clustering within therapist using ICCs.

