25.2 Follow up data collection

Participants will be followed for a total of 24 weeks. Follow up data collection will be conducted at 3 months (12 weeks) and 6 months (24 weeks) post-randomisation for both groups. We will operate strict "windows" for data collection. At three-month follow-up data collection window will operate from the start of week 11 to the end of week 14. If data is not collected within that time period, this is not pursued and the next time point will be focused on. The 6 month follow-up data collection window will operate from the start of week 23 to end of week 26.
Members of the RESPECT research team will arrange face to face appointments with participants; during these appointments the researchers will collect follow up data covering the main and secondary outcome measures.

The researchers will record missed appointments, as well as how many times they contacted (by text, phone or via case managers) to arrange follow-ups.

26. Qualitative data

There will also be qualitative interviews to gather data on acceptability and feasibility from the perspective of the participants using a sub-sample of consenting participants (see section 13)

27. Data related to fidelity to the intervention

At the end of each session, a short form will be completed by the clinicians delivering the intervention. This will list the content of the session with the clinician ticking what was covered during the session and space to make any additional notes or observations. In addition the participant will be invited to complete a very brief evaluation form.

28. Table of data collection schedule

Event	Time period	Data collected
Pre	Day 0	Consent for study; Baseline CRF:
		Feedback form for refusers

		Randomisation: including confirmation of consent; contact details; confirmation of baseline questionnaire completion
1	1-2 weeks	Intervention participants – First appointment: time of session; the length of session; participant attendance; therapist involved; location; and any materials used.
		Audio recording of sessions
2-6	2-12 weeks	Intervention participants subsequent appointments: time of session; the length of event; participant attendance; therapist involved; location; any materials used.
		Audio recording of sessions.
3	12 weeks	Three month CRF: follow-up.
4	24 weeks	Six month CRF: follow-up. Exit questionnaire

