39.1 Quantitative analyses

The flow of participants through the trial will be detailed in a CONSORT flow diagram. The number of people screened, randomly assigned, receiving the intervention, completing the study protocol and providing outcome data will be summarised overall and by trial arm. The number of individuals withdrawing from the intervention and/or the trial and any reasons for withdrawal will be summarised by trial arm. To quantify the acceptability of the intervention the number of sessions attended will also be summarised. All data will be presented descriptively with no formal statistical analyses undertaken. For each data collection point and outcome measure, the number of nonresponders will be calculated and completion rates compared. The potential impact of therapist effects may be explored using ICC and the average caseload per therapist will be detailed.

40. Analysis of economic and quality of life data

The economic component of the study will be designed to assess the feasibility of conducting a cost-effectiveness analysis of a full trial. This will involve piloting a short questionnaire, analysing responses and calculating Quality Adjusted Life Years (QALY) changes using the EQ-5D. We would not expect to see significant changes between groups due to the small sample size in this feasibility trial.

A simple questionnaire will measure participants' use of health care and will be identified retrospectively by means of service use questions. The economic analysis will assess the feasibility of using such a questionnaire in this population. The questionnaire will ask about primary care, sexual health and family planning services. In the full trial resource use data will be multiplied by national average unit costs to calculate per participant costs in the 3 month period before the intervention and the 3 month period after receiving the sexual health intervention or TAU.

Quality of life will be measured by EQ-5D at baseline and each follow up time point. The use of EQ-5D enables the estimation of QALYs. Measuring health status using QALYs follows the recommendations of NICE¹ and enables the value for money afforded by treatments to be compared to a range of other health care interventions.

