45.3 Risks and anticipated benefits for trial participants and society

The main risk from participating in the study is embarrassment regarding collecting data about sexual behaviour, and if receiving the intervention, discussing sexual health and relationships. In order to minimise this, potential participants will be informed of the specific nature of the study prior to consent. The research will be undertaken in a sensitive way, maintaining awareness of the vulnerability of many of the participants.

In terms of benefits to society, should this new intervention prove clinically and cost effective in a larger, multi-site trial and should it be widely implemented, it would have a significant impact on the sexual health of people diagnosed with SMI. The aim is to design and trial a realistic intervention that can be readily delivered even in a climate of cuts for treatment services. The scope for implementation and impact is therefore great.

46. Safety and Adverse events

There are no anticipated risks in relation to either arm of the trial. However, the research team are aware that some people who have experienced sexual abuse and exploitation may find participating in this study distressing and may trigger difficult feelings.

Distress management – if a participant expresses any signs or reports any distress during any study related activity (e.g. meeting with a member of research team or during intervention delivery) an immediate halt will be implemented to the activity. Study specific guidance will be used to guide the researcher or interventionist for the management of this situation. Incidences of low level distress will be reviewed during scheduled supervision meetings. If a participant is referred to the local mental health team for management of their distress the CI (or delegated research clinician) will be informed within 24 hours.

Adverse events – If a participant becomes unwell during the course of the study (irrespective of condition) and needs to be admitted as an inpatient or other adverse event occurs (self-harm, suicide attempt, violence to others or victim of violence) this will be reported to the CI (or delegated clinician) immediately on receipt of this information, and the chair of the DMEC within 48 hours. The Chair of the DMEC will have the authority to terminate the trial should there be evidence that the study is causing harm.

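### Read literally, the randomisation check admits only people who completed every baseline instrument, so baseline response per tool among those randomised is 100% by construction and says nothing about acceptability

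*Protocol*

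**What the plan says.** Three statements in the protocol tie randomisation to baseline data.

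- Section 22.1, opening sentence: patients who meet the eligibility criteria and "who provide written consent to take part in the study and provide baseline data will be eligible for randomisation".
- Section 22.1, information collected at randomisation: "Confirmation that all baseline data has been collected".
- Section 28, Day 0 row of the table: "confirmation of baseline questionnaire completion".

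Section 18 sets the order as consent, baseline assessment, randomisation. The term participant starts only at the last step: the researcher is to "randomise the patient (hereafter referred to as the participant").

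On the measurement side, Objective 1d in section 3.1 evaluates the data collection tools by "assessing overall questionnaire response rates and for each data collection tool". Section 39.1 carries this out: "For each data collection point and outcome measure, the number of nonresponders will be calculated and completion rates compared". Baseline is not excepted, and no denominator is named. Section 7 also plans to examine EQ-5D-5L completion and missing-data patterns over time. Section 45.3 explains why refusal is a live possibility: "The main risk from participating in the study is embarrassment regarding collecting data about sexual behaviour".

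**The concern.** Acceptability of the questionnaires is part of a main objective. Baseline is the first time anyone meets the sexual behaviour, stigma and condom instruments, so it is where refusal would first show. If randomisation requires every instrument to be completed, anyone who declines one is screened out before joining the group whose response is summarised. The baseline column of the completion table would then show full response for each tool, and a reader planning the main trial could take this as evidence that the tools are acceptable when it only reflects the entry check.

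The check also works as an entry condition applied after consent. It does not appear among the criteria in sections 13.1 and 13.2, while section 24 counts minimal exclusions among its safeguards against bias.

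**Working it through.** **The plan's own figure.** Section 33.1 gives 30% attrition with 100 participants as ±9 points, 21% to 39%. Check: 1.96 × √(0.30 × 0.70 / 100) = 0.0898, so 21.0% to 39.0%; and 100 × (1 − 0.30) = 70 measured. Both reproduce. They describe loss after randomisation and do not depend on the baseline check.

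**What the check does to the baseline rate.** Take the literal reading: a person is randomised only if every baseline instrument was completed. For any tool, baseline response among the randomised is (randomised who completed it) / (randomised) = 100/100 = 100%. The true refusal rate does not enter the expression, so the result carries no information about it.

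**Illustrative size.** The protocol gives no rate at which consenting people decline an instrument, so the rate q below is an assumption. I also assume that nobody drops out between consent and randomisation for any other reason. To randomise 100:

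- consents needed: C = 100 / (1 − q)
- consented, not randomised: C − 100
- lowest possible response for a single tool among all consenters: 100 / C = 1 − q (all decliners declined that tool)
- highest possible: 100% (none declined that tool)

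| q (assumed) | Consents C | Consented, not randomised | Response per tool among randomised | Possible response for a given tool among consenters |
|---|---|---|---|---|
| 0% | 100 | 0 | 100% | 100% |
| 5% | about 105 | about 5 | 100% | 95% to 100% |
| 10% | about 111 | about 11 | 100% | 90% to 100% |
| 20% | 125 | 25 | 100% | 80% to 100% |

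The fourth column never moves. The last shows what the two recorded totals can and cannot do: they bound the loss overall but cannot say whether one instrument or several caused it.

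**Whether another route in the protocol supplies the rate per tool.**

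- Section 16 records "how many of those screened were eligible and consent will be recorded and used to populate the CONSORT flow chart", and section 39.1 reports the number randomised. The difference is available, but it mixes questionnaire refusal with every other reason.
- The feedback form for people who returned a consent-to-contact form (sections 16 and 35) concerns recruitment, not individual instruments.
- The interview guide (section 36) covers the outcome measures, but section 35 draws about 20 interviewees from the two arms, so all have passed the check.
- The exit questionnaire (section 35) goes to people entered into the study.
- Response at 3 and 6 months is not gated. It comes from people already randomised, so it does not replace the baseline rate among consenters.

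None of these is described as recording which baseline instrument a non-randomised person declined.

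**The case against.** The strongest reply is that completeness is being read into the text. The opening sentence of section 22.1 asks only that baseline data be provided, and section 18 asks only that a baseline assessment be conducted. The checklist line may mean no more than that the baseline visit was finished before allocation. Section 29 expects little missing data at baseline and follow-up, not none, and section 39.1 counts non-responders at every time point, which fits a check that tolerates gaps. This has force. The literal reading rests on the checklist line and the table row, and even under it a completed instrument can have blank items, so item-level missingness could survive and be counted. But the protocol does not say that a declined instrument may be recorded as such and the person still randomised, and a site asked to confirm that all data are in has no instruction to do otherwise.

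It can also be said that the denominator, a CONSORT box and a tick-box belong in the SAP or case report form, which are not shown. That stands for the denominator taken alone. The check, however, is a protocol rule applied at randomisation, and an SAP cannot recover a reason for refusal that was not recorded at the visit.

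A reader might infer two stronger conclusions. One is that the trial cannot measure the acceptability of its questionnaires at all. The documents do not support this: the drop from consent to randomisation can be counted, follow-up response is ungated, and interviews ask about the measures. The other is that the attrition estimate is biased by a more compliant sample. No such bias is shown. Section 33.1 defines attrition among trial participants, which is the quantity needed for a main trial that also takes baseline before allocation.

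Finally, collecting baseline data before allocation is sound practice in an open trial and is not the fault.

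**Conclusion.** The concern holds in a limited form. If the section 22.1 check and the section 28 row are applied as worded, instrument-level baseline response among randomised participants is fixed at 100% and is uninformative for Objective 1d and section 39.1. What is lost is the rate of baseline refusal for each tool. The number of people involved is bounded by consented minus randomised: about 5 to 25 per 100 randomised if 5% to 20% decline an instrument, a range that is assumed because the protocol gives none. If sites read the check more loosely, the loss is smaller, but the baseline rate would then depend on unstated local practice. No sample-size figure changes. Because a main objective is touched and the remedy is cheap, the wording should be changed.

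**What to change.** 1. In section 22.1, replace the checklist line with: *baseline booklet administered before randomisation, with any declined instrument marked as declined*. Align the Day 0 row of the section 28 table, and state that declining an instrument does not bar randomisation. Baseline stays before allocation.
2. In section 39.1, report baseline completion for each tool with all consenting people as the denominator.
3. In the CONSORT diagram, add a step for people who consented but were not randomised, with the reason and, where relevant, the instrument declined.

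The cost is one checklist line, one table row, a declined box in the booklet and one CONSORT step. The drawback is that some randomised participants will have no baseline value on some instruments. That is tolerable here because section 39.1 plans descriptive presentation only, with no baseline-adjusted comparison to protect.
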